8.4 CT-guided Bone Biopsy (Arm 1)

A CT-guided biopsy of a bone metastasis that is deemed to be easy to biopsy and in an area without major risk for pathological fracture or bleeding will be taken during the biopsy visit. Patients will receive routine local anaesthetic of the region to be biopsied followed by thorough disinfection of the biopsy site with antiseptic wipes. Patients will be asked to fast on the day of the procedure and to have an intravenous cannula inserted to allow the use of medication causing minimal sedation (for example midazolam and/or fentanyl) during the procedure if required to alleviate discomfort or pain. For biopsy sampling the Arrow® OnControl® Powered Bone Access System (Teleflex, USA) will be used. In patients with greater than one bone metastasis assessed as amenable to bone biopsy, biopsies will be obtained from a maximum of two sites of bone metastases. A maximum of three specimens from each biopsy site will be taken. Samples will be examined on site by a histopathologist to warrant collection of high-quality material and advise the sampling as needed. Maximum duration of procedure will be 45-60 min.

Following the bone biopsy, the patient will be observed in the Radiology Department to be assessed for any excessive bleeding before transferring.

8.5 TRUS-guided Targeted Transperineal Prostate Biopsy (Arm 1)

Transperineal Prostate Biopsy will be performed following standard clinical practice of local department. This will include pre-operative oral analgesia and prophylactic antibiotic treatment according to local hospital policy for transperineal prostate biopsies.

Patients will be placed in lithotomy position and the scrotum will be carefully taped out of the way. As per local hospital practice the procedure may - at the discretion of the performing surgeon - involve application of topical ointment (ie 2% diltiazem) to relax the anal sphincter, insertion of a transurethral catheter for the procedure and/or the use of a local lidocaine-containing gel (Instillagel) inserted into the patients back passage and applied to the anus to alleviate discomfort related to the ultrasound probe. The perineal skin will be cleaned with an antiseptic solution. An ultrasound probe is then passed into the back passage, which will remain there for the duration of the procedure to visualise the prostatic gland to guide perineal sampling. In order to numb the perineum and prostate as much as possible, a local anaesthetic will then be injected underneath the skin and into the deeper tissue layers guided by ultrasound. Systematic and targeted core biopsies from the prostate will be acquired. In addition to core biopsies required for standard of care diagnostic purpose, lesions seen on a mpMRI (if available) will be targeted to allow a minimum of 4 core biopsies from any detected lesion as well as at least 2 core biopsies from uninvolved prostate tissue. Otherwise cognitive biopsies guided by ultrasound will be obtained. If a second prostate lesion is detected, core biopsies will also be acquired from this lesion. In total, in addition to any core biopsies required as standard of care a maximum number of 8 to 12 additional prostate core biopsies will be taken for research purposes. Maximum duration of procedure will be 60 minutes.

8.6 Radical Prostatectomy (Arm 2)

Radical Prostatectomy will be performed according to standard of care robotic approach used at The Christie Hospital and as relayed to the patient by the attending urologic surgeon. The side effects of the surgery are the ones reported in the literature and the latest participant information leaflet provided prior patient consent (e.g. risk of erection dysfunction, incontinence, etc.).

The current study will not imply any change of the current surgical procedure as standard of care conducted routinely at the Christie Hospital. It will not increase the incidence of known potential co-morbidities already described in general for a radical prostatectomy nor instructions to the patient by the attending urologic surgeon.

8.7 Blood Sampling

For patients in Arm 1 - A blood sample for research purposes will be withdrawn at the each of the following visits:

(i) Baseline visit (pre- pimonidazole)

- 2 x 10mL *Streck cell-free DNA blood collection tubes*® for circulating tumour cell (CTC) collection and circulating tumour DNA (ctDNA) extraction.
- 1-2 x 3.5mL blood samples collected into EDTA tubes for germ line DNA extraction and processing to PBMC for banking and future profiling of immune cell populations
- 1 x 10mL serum tubes for future, biobank related research projects, ie lipidomics, metabolics and microRNA analysis

(ii) Biopsy visit (pre-biopsy)

- 2 x 10mL *Streck cell-free DNA blood collection tubes*® for circulating tumour cell (CTC) collection and circulating tumour DNA (ctDNA) extraction.
- 1 x 10mL serum tubes for future, biobank-related research projects, ie lipidomics, metabolics and microRNA analysis

(iii) Follow up visit (within 6 months post-treatment, for patients 11-30)

- 2 x 10mL *Streck cell-free DNA blood collection tubes*® for circulating tumour cell (CTC) collection and circulating tumour DNA (ctDNA) extraction.
- 1-2 x 3.5mL blood collected into EDTA tubes for germline DNA extraction and processing to PBMC for banking and future analysis of immune cell populations
- 1 x 10mL serum tubes for future, biobank related research projects, ie lipidomics, metabolics and microRNA analysis

For Patients in Arm 2

A blood sample (maximum 20ml) will be taken for standard of care blood tests prior to prostatectomy including Full Blood Count, Renal Function and PSA. At the same time these standard of care bloods are taken, additional bloods - a maximum of 30ml – will be taken for research purposes as required for the following downstream analysis:

- Germ line DNA extraction and optional processing to PBMC for banking and future profiling of immune cell populations
- Biobank related research projects, ie lipidomics, metabolics and microRNA analysis

8.8 Whole-body MRI (Arm 1)

For patients within Arm 1, Whole-body MR imaging (wbMRI) will be performed once, before or after the biopsy study visit, depending on available examination slots in the Department of Radiology at The Christie NHS Foundation Trust. wbMRI images will allow comparison of the numbers of bone metastases detected by routine bone scan and wbMRI for sensitivity assessment of both techniques for oligometastatic disease.

MR Sequences acquired following Christie Hospital Whole Body MRI Image Acquisition Guidelines. The wbMRI scan is estimated to last around 70 minutes.

vist

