6 BACKGROUND

6.1 Background

Metastatic prostate cancer

Prostate cancer is the most common malignancy in men and the second commonest cause of cancer-related deaths in Western countries. Around 47,700 patients will be diagnosed with prostate cancer (PCa) in the UK each year [1]. About 15% present with primary M1 disease, which remains incurable despite remarkable improvements of treatment over the last decade. Interestingly, about 60% of M1 patients show solely metastasis to the bone sparing lymph nodes and any other organs. However, there is a paucity of data explaining both, early metastatic spread and the preference of prostate cancers to metastasise to the bones.

Oligometastatic disease

Oligometastatic solid tumours refers to a stage with a limited number of metastases and is perceived to be a distinct subtype of malignancy where more aggressive or at least more effective treatment holds promise to sustainably eradicate all lesions and thus to be curative [2]. For PCa, oligometastatic disease has not yet been adopted as an own subtype of disease, but it can be defined as the presence of ≤ 4 non-locoregional metastases. Recently, the STAMPEDE study reported a remarkable survival improvement by the addition of radiotherapy of the prostate to androgen-deprivation as standard of care in patients with a maximum of 4 bone metastases as identified by routine bone imaging, which is why we decided to apply a cut-off of ≤ 4 bone metastases on routine bone scintigraphy to define a PCa as being oligometastatic [3]. Consequently, novel targeted, biomarker-driven treatment approaches may ultimately help to improve treatment success, particularly in oligometastatic PCa.

Tumour hypoxia

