8 STUDY PROCEDURES & METHODOLOGY

8.1 Study Design

This is a prospective, non-randomised, single-centre, exploratory biomarker study. In Arm 1 this involves targeted tumour tissue sampling in men with either newly diagnosed, untreated metastatic prostate cancer involving patients with either high (cohort A; widespread metastatic disease) or low, oligometastatic (cohort B; ≤ 4 bone metastases) burden of disease. In Arm 2, targeted tumour tissue samples derived from prostate cancers biobanked as per standard MCRC biobanking protocol in 30 men undergoing a radical prostatectomy as part of their standard care.

In Arm 1, to minimize the interventional burden for the patients, patients will be amenable to have a combined diagnostic and research biopsy of the prostate in one session after routine imaging for diagnostic work-up comprising of a CT scan of abdomen and pelvis, bone scan and multi-parametric MRI of the prostate. Patients, who already had a diagnostic TRUS biopsy will be asked to provide research tissue samples during a second TRUS biopsy as part of the HYPROGEN study interventions. Patients declining a second prostate biopsy will be eligible and will undergo the bone biopsy only. Patient identification will be done through the respective multidisciplinary tumour (MDT) boards and patient referral pathways at Salford Royal, Oldham Royal and Wythenshawe Hospital as further outlined in section 9.1.

To yield highest possible biopsy accuracy and tissue amount and maximum procedure safety, prostate biopsy will be a TRUS-guided targeted transperineal biopsy and bone biopsy will be CT-guided using an automated drill. Moreover, to identify the imaging modality with the highest accuracy in detecting bone-metastatic prostate cancer at first presentation, an additional whole-body MRI will be applied to patients on the study. Study participation will not affect the routine care for this stage of disease, which will start immediately after the biopsy samples have been acquired.

In Arm 2 tumour tissue samples will be acquired from prostatectomy specimens that patients are undergoing as part of their routine standard of care.

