8.3 Patient Benefit and Overall Risk

This is a prospective, translational, exploratory biomarker study, which is why there will be no direct benefit derived from the data obtained for the individual PCa patient participating in this study. However, this study may ideally lead to the identification of tumour hypoxia and its related aberrations as a therapeutic target in (oligo-)metastatic PCa in the near future. Results of the HYPROGEN study will not affect treatment according to the current standard of care including - for patients in Arm 1 - androgen deprivation with or without more intensified treatment including docetaxel, abiraterone acetate plus prednisone and/or irradiation of the prostate.

Within Arm 1 Patients who are enrolled onto this study will need to make four additional outpatient visits to the hospital for the duration of the study (consent, biopsy, imaging, and follow up visit).

Patients entering this study will undergo additional imaging with a whole-body MRI as well as additional biopsies of tissues affected by their cancer at two body areas as well as additional blood sampling for research purposes. The tissue biopsy sites include the prostatic gland and the bones. There may be side effects associated with these biopsies.

The additional whole-body MRI scan will help to further define the sensitivity of routine bone scanning and MRI scanning to detect a metastatic state.

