8.9 Prostate MRI scans (Arm 2)

Patients within Arm 2 will be offered the option to undergo additional MR imaging of the pelvis in addition to any standard of care imaging acquired. In patients who agree to undergo additional scans, MRI scans will be performed on 2 occasions prior to the radical prostatectomy. MRI scans will be acquired on either the MR sim diagnostic scanner, on the MR Linac scanner or on both within The Christie NHS Foundation Trust.

The MR sequences obtained will include sequences for oxygen-enhanced MR, IVIM, DCE and BOLD and aim to detect hypoxic sub-regions of tumour that can be validated against pimonidazole staining regions following prostatectomy. Patients will be asked to will breathe 21% followed by 100% oxygen gas through an oxygen mask during the scan. They will receive a gadolinium-based contrast agent through an intravenous cannula. Scan time will not exceed 60 minutes per scan. Any patients not agreeing to undergo additional MRI scans are still able to be enrolled into Arm 2 of the trial.

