9.2 Sample Size

A total number of 60 patients will be recruited into this pilot study, 30 patients with metastatic disease in Arm 1 and 30 patients with localised prostate cancer in Arm 2. Within Arm 1, 15 patients with a high disease burden identified as a number of bone metastases ≥ 5 with or without visceral metastases (cohort A) and 15 with a low burden of bone metastases defined as ≤ 4 bone metastases and no signs of visceral disease (cohort B) detected on routine bone scan imaging. As this is a feasibility study, no power calculation was applied for patient number estimation.

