9.4 Inclusion Criteria

Arm 1

No	Inclusion Criteria Patients are eligible only if they meet all of the following criteria
1	Male patients aged 18 years and older
2	Histologically proven adenocarcinoma of the prostate (\geq cT2) OR Highly suspected metastatic prostate cancer
3	PSA value of \geq 20 ng/mL
4	Multiple lesions (\geq 5) suspicious of metastatic spread on routine imaging procedures with at least one amenable* to biopsy (cohort A) OR oligometastatic bone disease (\geq 1 to \leq 4) at routine bone scan with at least one lesion amenable* to biopsy (cohort B) *e.g. safely to biopsy and expectably providing sufficient tissue yield
5	World Health Organisation (WHO) performance status 0 to 2 with no deterioration over the previous 2 weeks and minimum life expectancy of 12 months
6	No prior local and/or systemic treatment for localised prostate cancer
7	Willing to donate cancer tissue samples for research purposes (bone metastasis and primary tumour)

Arm 2

No	Inclusion Criteria Patients are eligible only if they meet all of the following criteria
1	Male patients aged 18 years and older cT ₂ -T ₃ / cN ₀ -N ₁ / cM ₀ Any Group Grade (GG) 2-5: this includes Gleason scores 3+4, 4+3, 4+4, 4+5, 5+3, 5+4, 5+5. Any PSA
2	Histologically proven adenocarcinoma of the prostate
3	Planned radical prostatectomy as primary treatment for localised prostate cancer
4	World Health Organisation (WHO) performance status 0 to 2 with no deterioration over the previous 2 weeks and minimum life expectancy of 12 months
5	No prior local and/or systemic treatment for localised prostate cancer
6	Willing to donate cancer tissue samples for research purposes (any metastasis and primary tumour)

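### The Arm 1 imaging comparison is described as testing accuracy and sensitivity, but the design supports only a descriptive comparison of bone-lesion counts, conditional in cohort B on the bone-scan entry rule

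*Protocol*

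**What the plan says.** Three places in the protocol state what the Arm 1 wbMRI is for:

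- Section 8.1: "to identify the imaging modality with the highest accuracy in detecting bone-metastatic prostate cancer at first presentation".
- Section 8.8: "comparison of the numbers of bone metastases detected by routine bone scan and wbMRI for sensitivity assessment of both techniques for oligometastatic disease".
- Section 8.3, more softly: the scan will "help to further define the sensitivity of routine bone scanning and MRI scanning to detect a metastatic state".

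The entry rules decide who is scanned. Section 6.1 uses a cut-off of at most four "bone metastases on routine bone scintigraphy to define a PCa as being oligometastatic". Section 9.4 admits cohort B with 1 to 4 lesions "at routine bone scan with at least one lesion amenable* to biopsy (cohort B"). Cohort A needs five or more lesions "suspicious of metastatic spread on routine imaging procedures with at least one amenable* to biopsy (cohort A"), a wider basis that does not name the bone scan. Section 9.2 plans 15 men per cohort and ends its description with "detected on routine bone scan imaging".

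wbMRI is done in Arm 1 only. Arm 2, the M0 arm, is offered "additional MR imaging of the pelvis" (section 8.9). Section 8.4 limits bone biopsy to two metastatic sites per man, and section 8.3 gives its role as confirming disease already seen on imaging.

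On timing, section 8.2 places wbMRI in a window of 10-15 working days that follows the biopsy, starts standard treatment one day after the biopsy visit, and ends the study once the last man has had his follow-up visit. Section 8.8 lets the scan fall on either side of the biopsy. Section 11.12 places androgen deprivation and chemotherapy after the study has ended.

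**The concern.** Sensitivity is the share of truly diseased men, or truly metastatic lesions, that a test detects. Accuracy also needs the test's behaviour where disease is absent. To compare two tests on either measure, the sample should not be chosen by the result of one of them, and there should be some way to tell true from false findings.

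In cohort B the sample is chosen by the bone scan. A man whose bone scan shows nothing cannot enter, and neither can a man whose bone scan shows five or more lesions. A sensitivity reported from these men would partly reflect the entry rule. A ranking by accuracy would have no planned disease-negative denominator. Only the imaging conclusion is at stake; the genomic and hypoxia aims are untouched.

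**Working it through.** The protocol gives no accuracy, precision or power figure to reproduce. Its totals add up: 15 + 15 = 30 in Arm 1 and 30 + 30 = 60 overall.

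**1. Patient level, cohort B.** Every man has at least one bone-scan lesion by rule, so the bone scan is positive in 15/15 = 100% whatever its true sensitivity. The exact 95% lower limit, 0.025^(1/15) = 78.2%, would look like evidence but describes only the entry rule.

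**2. Lesion level, cohort B (illustration; every input is assumed).** Let a man have N true lesions, N uniform on 1 to M, each detected independently by bone scan with probability p, so that X ~ Bin(N, p). He enters if 1 ≤ X ≤ 4. The pooled apparent sensitivity is

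Σ_N E[X; 1 ≤ X ≤ 4] / Σ_N N·P(1 ≤ X ≤ 4).

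For M = 4 and p = 0.6 the numerator is 0.6 + 1.2 + 1.8 + 2.4 = 6.0. The denominator is 1(0.600) + 2(0.840) + 3(0.936) + 4(0.9744) = 8.99. The ratio is 66.8% against a true 60%.

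| True p | M = 4 | M = 6 | M = 8 |
|---|---|---|---|
| 40% | 53.2% (+13.2) | 46.4% (+6.4) | 42.2% (+2.2) |
| 60% | 66.8% (+6.8) | 60.7% (+0.7) | 56.3% (-3.7) |
| 80% | 82.6% (+2.6) | 76.9% (-3.1) | 74.6% (-5.4) |

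The lower entry limit pushes the estimate up and the cap at four pushes it down, so the sign depends on a lesion mix that is not known. Eight of the nine shifts are below 7 points.

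**3. Disease-negative men.** wbMRI is planned in Arm 1 only, where all men are imaging-positive at entry. The number of men planned as disease-negative and scanned by wbMRI is 0, so patient-level specificity has no planned denominator.

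**4. Histology.** With at most two sites biopsied among L lesions, the largest verifiable share is min(2, L)/L: 100% for 1-2 lesions, 67% for 3, 50% for 4 and 40% for 5. As an example, suppose the bone scan shows 3 lesions and wbMRI shows 5, with three shared and real. Bone-scan sensitivity is 3/5 = 60% if the two extra lesions are real and 3/3 = 100% if they are false.

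**5. Timing (a separate matter).**

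| Topic | Section 8.2 | Other section |
|---|---|---|
| wbMRI | after biopsy, in a 10-15 working-day window | 8.8: either side of biopsy |
| Treatment | one day after biopsy, while the study is running | 11.12: after the study ends |

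Under 8.2 a scan can fall up to about 15 - 1 = 14 working days after treatment starts. Under 8.8 it may come before both biopsy and treatment.

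**The case against.** The strongest reply is that little hangs on this. The study is an unpowered pilot, the comparison is not among the section 7 aims or the 6.4 hypotheses, and 8.8 promises only that the images will allow counts to be compared. That stands, and it keeps the point minor. It does not rescue the labels: a small sample explains imprecision, but enlarging this one would not make accuracy estimable.

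Several stronger readings are tempting, and the protocol does not support them.

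- **That all of Arm 1 is selected on the bone scan.** Section 9.4 admits cohort A on routine imaging in general, which under 8.1 includes CT and prostate MRI. The closing phrase of 9.2 may qualify cohort B alone, so it settles nothing for cohort A, and no firm conflict between 9.2 and 9.4 can be claimed.
- **That the lesion-level bias is known to be large.** The figures rest on assumed inputs and are small beside sampling error. With 15 men, 5/15 has an exact 95% interval of 12-62%.
- **That no specificity of any kind could be derived.** Negative regions within positive men, or a chance biopsy-negative result, remain possible. The gap is at patient level.
- **That the lack of a named reference standard is an error.** This may sit in a SAP or imaging plan, and routine CT and MRI could contribute to a reference. The limit stated here concerns histology only. If wbMRI came before biopsy, a lesion seen only on wbMRI could be targeted, but two sites per man would still be the ceiling.
- **That treatment before wbMRI distorts the counts.** The protocol gives no such effect and none is claimed.

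On 11.12, the end of the study might be meant as the end of one man's procedures. Section 8.2 defines it otherwise, so the texts conflict as written.

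**Conclusion.** The point holds in limited form and is minor. Sections 8.1 and 8.8 name properties that the Arm 1 design does not deliver.

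Three facts follow from the protocol alone: 15/15 bone-scan positivity in cohort B by construction, no planned disease-negative men with wbMRI, and at most two histologically verified bone sites per man. The lesion-level shift of about +13 to -5 points rests on independent detection, one common p and a uniform lesion mix. It shows only that the direction cannot be known in advance.

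A reader might infer that the comparison has no value. It has: counting wbMRI lesions in men whom the bone scan calls oligometastatic is coherent and useful when described as that. The two timing conflicts are real on the page but separate from this argument.

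**What to change.** In 8.1 and 8.8, and in 8.3 for consistency, replace the accuracy and sensitivity wording with a descriptive paired comparison of bone-lesion counts, wbMRI against bone scan, reported by cohort. For cohort B, state that it is conditional on the bone-scan entry rule. One useful summary would be the proportion of cohort B men with five or more lesions on wbMRI. Claim histological confirmation only for lesions that were biopsied.

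Separately, the sponsor should reconcile 8.2 with 8.8 on wbMRI timing and 8.2 with 11.12 on treatment timing; this review does not say which text is right. The date of each wbMRI relative to biopsy and treatment start should be recorded.

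The cost is protocol wording and one recorded item, with no extra scans or patients. The imaging claim becomes more modest, and precision stays low: with 15 men the 95% half-width for a mean paired difference is t(0.975, 14)/√15 = 0.55 SD.
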